## **11.1 Efficacy and Pharmacodynamic Assessments**

#### **11.1.1 Efficacy Assessment**

Efficacy will be evaluated in terms of overall response rate (ORR) (sCR + CR + VGPR + PR) (Kyle 2009), further tumor response rates (CR, sCR PR, MR, VGPR), SD rate, duration of response, TTP, and PFS, using the modified European Group for Blood and Marrow Transplantation (EBMT) criteria (Blade 1998) plus the International Myeloma Working Group Uniform Response Criteria (2006), taking the supplement by Kyle (Kyle 2009) into consideration.

All of these tumor response criteria for MM are defined in Appendix 18.3. All of them are based on the International Myeloma Working Group Uniform Response Criteria (Durie 2006 and

Erratum 2007), except for MR, which is based on the EBMT criteria (Blade 1998). Disease progression is defined as progressive disease according to the IMWG, 2006 (see Appendix 18.3, Table 14), death or start of new anti-MM treatment.

All responses need two consecutive assessments, ideally being confirmed at Day 1 of the next cycle.

The response evaluation will be based on serum and urine M-protein levels, serum FLC level, and FLC ratio.

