#### Table 11Laboratory Evaluations

^a Provided sufficient quantities of serum are available, additional measurements of tetanus titer will be performed by central laboratories

 $^{\rm b}$  β2-microglobulin measured at screening only

The signed and interpreted laboratory results will be kept as supplemental pages to the subject's eCRF.

With the exception of pharmacokinetic parameters, anti-MOR03087 antibodies, cytokines, CD16 expression, and flow cytometry, all clinical laboratory parameters (see Table 11) will be analyzed at the local hospital laboratories. Samples for M-Protein and FLC will be analyzed centrally in order to be able to evaluate potential variances and to assess additional time points. Tetanus titers will be analyzed by a central laboratory. All blood samples will be processed and handled according to standard laboratory procedures.

Serum samples will be collected for pharmacokinetic parameters (MOR03087), anti-MOR03087 antibodies and cytokines and stored at -20°C or below at the study site until shipment on dry ice to the external analytical laboratory. At the analytical laboratory, the samples will also be stored at -20°C or below until analysis.

Plasma samples will be collected for pharmacokinetic parameters (LEN or POM) and stored at -70°C at the study site until shipment on dry ice to the external analytical laboratory. At the analytical laboratory, the samples will also be stored at -70°C or below until analysis.

Detailed instructions for sample handling will be provided in the laboratory manual.

Before the initial administration of study drug (MOR03087, POM, or LEN), the respective inclusion and exclusion criteria defined in Sections 8.1 and 8.2 should be followed. For all administrations of MOR03087, the following parameters should be taken predose on the day of study drug administration and, if outside the limits described below, administration of MOR03087 should be postponed (see Section 8.6):

Value	Subject should not be dosed if the value is:
Creatinine	> 3 × ULN
Hemoglobin	< 8.0 g/dL (subject should be transfused before dosing)
Platelets	$< 25.0 \times 10^{9}$ /L (< 30.0 × 10 ⁹ /L in the LEN and POM parts)
WBC	$< 1.0 \times 10^{9}/L$
Potassium	> 6.0 mmol/L
Sodium	> 155 mmol/L
AST/ALT	$> 3 \times ULN$

POM, LEN or DEX may have to be interrupted and/or dose reduced as well, according to Section 9.1.4.

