### **15.7.3 Clinical Laboratory Evaluations**

The analysis of laboratory parameters will be presented separated into blood parameters (hematology, serum chemistry, endocrinology, coagulation) and urine parameters (urinalysis). All data will be listed.

For hematology and serum chemistry, the laboratory values will be transformed to SI values based on SI units to make laboratory parameters comparable between different local laboratories. The relevant reference ranges supplied by each laboratory will also be transformed to SI reference ranges for each laboratory.

Descriptive summaries of actual (absolute) values and changes from baseline values will be presented for hematology and serum chemistry by treatment arm and dose level for the Safety Population.

Each abnormal value will be flagged to show whether it is a value below or above the reference range. For the assessment of laboratory variables, five categories will be used that determine the investigator's assessment of clinical relevance: 'clin. rel., above', 'non-clin. rel., above', 'within', 'non clin. rel., below', 'clin. rel., below'.

The assessment of laboratory variables will be tabulated by time point for each clinical laboratory analyte for the Safety Population by treatment arm and dose level (frequency tables). Additionally, for each laboratory parameter, shifts in assessments from baseline to all

post-administration time points will be presented for the recommended dose groups of each treatment arm (shift tables).

Grades for a clinical laboratory analyte will be derived according to NCI CTCAE, version 4.0 and used to present additional frequency and shift tables based on NCI CTCAE grades.

The assessment of categorical urinalysis variables will be tabulated by time point for each urine parameter for the Safety Population by part and dose level (frequency tables). Additionally, for each of these urine parameters, shifts in assessments from baseline to all post-administration time points will be presented for the recommended dose groups of each treatment arm (shift tables).

Laboratory values that are outside the reference range will also be flagged in the data listings, along with corresponding reference ranges.

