PD	
 
NOTE: Requires any one or more of the following: Increase of ≥ 25% from nadir in
 
Serum M-component and/or (absolute increase must be ≥ 0.5 g/dL)^g
 
Urine M-component and/or (absolute increase must be ≥ 200 mg/24 hours)
 
Only in patients without measurable serum and urine M-protein levels: the difference between involved and uninvolved FLC levels. Absolute increase must be > 10 mg/dL.
 
Bone marrow plasma cell percentage: absolute % must be ≥ 10%^h
 
Definite development of new bone lesions or soft tissue plasmacytomas or definite increase in the size of existing bone lesions or soft tissue plasmacytomas
 
Development of hypercalcemia (corrected serum calcium > 11.5 mg/dL or 2.65 mmol/L) that can be attributed solely to the plasma cell proliferative disorder
 

Table 14Response Criteria for Multiple Myeloma

Abbreviations: CR = complete response; FLC = free light chain; MR = minimal response; PD = progressive disease; PR = partial response; SD = stable disease; VGPR = very good partial response

- ^a All response categories require two consecutive assessments made at any time before the institution of any new therapy; all categories also require no known evidence of progressive or new bone lesions if radiographic studies were performed. Radiographic studies are not required to satisfy these response requirements.
- ^b Confirmation with repeat bone marrow biopsy not needed.
- ° Presence/absence of clonal cells is based upon the  $\kappa/\lambda$  ratio. An abnormal  $\kappa/\lambda$  ratio by immunohistochemistry and/or immunofluorescence requires a minimum of 100 plasma cells for analysis. An abnormal ratio reflecting presence of an abnormal clone is  $\kappa/\lambda$  of >4:1 or <1:2.
- ^d MR also includes subjects in whom some, but not all, the criteria for PR are fulfilled, provided the remaining criteria satisfy the requirements for MR.
- ^e The response criterion MR will not apply to subjects who present with serum FLCs only.
- ^f Per the International Myeloma Working Group Uniform Response Criteria (Durie 2006), stable disease is not recommended for use as an indicator of response; stability of disease is best described by providing the time to progression estimates.
- ^g For progressive disease, serum M-component increases of  $\geq 1$  g/dL are sufficient to define relapse if starting M-component is  $\geq 5$  g/dL.

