## 18.6 International Staging System (ISS) Criteria and Durie-Salmon Staging Criteria

Details of multiple myeloma staging are provided according to the International Staging System (Table 17) and the Durie-Salmon criteria (Table 18). Staging should be performed at the time of screening.

Table 17	Criteria for International Staging System (ISS)
----------	-------------------------------------------------

Stage I	$\beta$ 2-microglobulin ( $\beta$ 2M) < 3.5 mg/L, albumin $\geq$ 3.5 g/dL
Stage II	$\beta 2M < 3.5 \text{ mg/L}$ and albumin < 3.5 g/dL; or $\beta 2M 3.5-5.5 \text{ mg/L}$ irrespective of the serum albumin
Stage III	$\beta 2M \ge 5.5 \text{ mg/L}$

Stage	Criteria	Measured Myeloma Cell Mass ^a
Stage I (low cell mass)	
 
All of the following:
 
Hemoglobin value >10 g/dL
 
Serum calcium value normal or <10.5 mg/dL
 
Bone x-ray, normal bone structure (scale 0), or solitary bone plasmacytoma only
 
Low M-component production rates IgG value <5 g/dL; IgA value <3 g/dL
 
Urine light chain M-component on electrophoresis <4 g/24h
 
	600 billion
Stage II (intermediate cell mass)	Fitting neither Stage I nor Stage III	600 to 1,200 billion
Stage III (high cell mass)	
 
One or more of the following:
 
Hemoglobin value <8.5 g/dL
 
Serum calcium value >12 mg/dL
 
Advanced lytic bone lesions (scale 3)
 
High M-component production rates IgG value >7 g/dL IgA value >5 g/dL
 
Bence Jones protein >12 g/24h
 
	>1,200 billion
Subclassification (either A or B)	
 
A: relatively normal renal function (serum creatinine value) <2.0 mg/dL
 
B: abnormal renal function (serum creatinine value) >2.0 mg/dL
 
Examples: Stage IA (low cell mass with normal renal function) Stage IIIB (high cell mass with abnormal renal function
 
	

Table 18	Criteria for Durie-Salmon Staging
----------	-----------------------------------

^a Myeloma cells in whole body, in billions/m²

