7.3.3 Efficacy Endpoints Based on Investigator Assessment

The Investigator will assess efficacy at specific study visits according to the response criteria for MM as defined in section 18.3 of the study protocol version valid at the time of the assessment. All of the criteria are based on the International Myeloma Working Group (IMWG) Uniform Response Criteria [6], except for MR, which is based on the (adopted) European Group for Blood and Marrow Transplantation (EBMT) criteria [7].

The response evaluation of the Investigator is based on the serum and urine M-protein levels, and, where applicable, the serum FLC level, and FLC ratio.

The categories of overall tumor response assessment of the Investigator will be as follows:

- sCR – Stringent Complete Response
- CR - Complete Response
- VGPR - Very Good Partial Response
- PR - Partial Response
- MR - Minimal Response
- SD - Stable Disease
- PD - Progressive disease
- Missing (if response assessment is not done)

In case of progressive disease, the date of progression will be given by the Investigator.

All responses need 2 consecutive assessments, ideally being confirmed at Day 1 of the next cycle. Thus all endpoints defined to evaluate responses per-subject across time points (see section 7.3.3.2 and 7.3.3.3) will include confirmed responses only.

For all endpoints where dates are used in the derivations (e.g. date of first response, date of first

progression), the following dates will be taken into consideration to determine the time point each response assessment refers to:

- Date of assessment or date of visit, whichever is earlier if the assessment is non-PD (this approach is chosen as the assessment is sometimes done retrospectively and not at the date of the visit)
- date of progression given by the Investigator in the field “Date of Progression” in the response assessment form if the assessment is PD

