10.3 Clinical Laboratory Evaluations

Safety laboratory data (hematology, serum chemistry, endocrinology, coagulation, urinalysis) will be analyzed by the respective local laboratories of each involved site.

The analysis of safety laboratory parameters will be presented separated into blood parameters (hematology, serum chemistry, endocrinology, coagulation) and urine parameters (urinalysis). All data will be listed.

The blood parameters will be transformed to SI values based on SI units to make laboratory parameters comparable between different local laboratories. The relevant reference ranges supplied by each laboratory will also be transformed to SI reference ranges for each laboratory.

Descriptive summaries of actual (absolute) values and changes from baseline values will be presented for all blood parameters.

Creatinine clearance will be calculated according to the Cockcroft-Gault formula and will be included in descriptive summaries of actual (absolute) values and changes from baseline.

Each abnormal value will be flagged to show whether it is a value below or above the reference range. For the assessment of laboratory variables, 5 categories will be used that take into account

the investigator's assessment of clinical relevance: 'clinically relevant, above', 'non-clinically relevant, above', 'within', 'non-clinically relevant, below', 'clinically relevant, below'.

The assessment of laboratory variables will be tabulated by time point for each clinical laboratory analyte (frequency tables).

If NCI-CTCAE grades are available for a clinical laboratory analyte, these will be derived according to NCI-CTCAE version 4.0 and used to present additional frequency based on NCI-CTCAE grades.

For hematology parameters, shifts in assessments from baseline to worst-post baseline will be presented based on classifications relative to the laboratory reference ranges (low/normal/high) for hematology parameters where NCI-CTCAE grades are not defined. If a subject experiences both "Low" and "High" assessments in the course of the trial, the worst post-baseline will be defined as "Low and High".

If NCI-CTCAE grades are available for a hematology parameter, frequency, shift and summary tables based on grades will be created as follows:

- Incidence of subjects with worst post-baseline grade. Each subject will be counted only for the worst grade
- Shift tables to compare baseline to the worst post-baseline value using CTCAE grades

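### The hypercalcemia criterion for progressive disease prints two calcium limits as if equivalent, but 11.5 mg/dL is 2.87 mmol/L and 2.65 mmol/L is 10.6 mg/dL, so a progression call may depend on the unit read

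*Protocol*

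**What the plan says.** Protocol Section 18.3, Table 14, lists the ways in which a subject can reach progressive disease (PD). The entry "Requires any one or more of the following", so a single criterion is enough. One of them is new hypercalcemia, with corrected serum calcium above "11.5 mg/dL or 2.65 mmol/L) that can be attributed solely to the plasma cell proliferative disorder". The table does not say which of the two figures governs.

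The table is the working definition of progression:

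- Protocol 11.1.1: "Disease progression is defined as progressive disease according to the" published working-group criteria as set out in Table 14. Death and the start of new anti-myeloma treatment are added as further routes.
- SAP 7.3.3: "The Investigator will assess efficacy at specific study visits according to the response criteria for MM as defined in section 18.3". The protocol version in force at the time applies, and the investigator also supplies the date of progression.

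Calcium belongs to the serum chemistry panel in Protocol Table 11. Apart from a few named assays, "all clinical laboratory parameters (see Table 11) will be analyzed at the local hospital laboratories". Calcium is not among the exceptions.

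Units are harmonised only for the laboratory analysis. Protocol 15.7.3 says of the hematology and chemistry panels that "the laboratory values will be transformed to SI values based on SI units to make laboratory parameters comparable between different local laboratories", and SAP 10.3 repeats this for the blood parameters.

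**The concern.** A threshold printed in two units should describe one concentration. These two do not, and nothing in either document brings them together at the point where the investigator decides. The SI conversion in Protocol 15.7.3 and SAP 10.3 serves the laboratory summaries and does not reach the response assessment.

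The PD call determines or influences PFS, TTP, duration of response, duration of clinical benefit, event-free survival and best overall response (SAP 7.3.3.2 and 7.3.3.3). Protocol 7.1 and 10.1.13 also tie continued treatment to progression, although they allow dexamethasone to be added after four cycles in a subject with PD who is not already receiving it. The recommended-dose groups may hold as few as 9 subjects (Protocol 15.9, SAP 5). There, one event gained or lost is 1/9, about 11% of the group.

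**Working it through.** **Inputs.** The two limits, 11.5 mg/dL and 2.65 mmol/L, come from Protocol Table 14. The molar mass of calcium, 40.078 g/mol, is a physical constant that the documents do not give. It is taken as an assumption, with 40.0 to 40.1 tried as a range.

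**Formula.** mmol/L = (mg/dL × 10) / molar mass; mg/dL = (mmol/L × molar mass) / 10.

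1. The mg/dL limit in SI units: 11.5 × 10 / 40.078 = 115 / 40.078 = 2.869, or 2.87 mmol/L (range 2.868 to 2.875). The printed 2.65 mmol/L is not reproduced.
2. The SI limit in conventional units: 2.65 × 40.078 / 10 = 10.62, or 10.6 mg/dL (range 10.60 to 10.63). The printed 11.5 mg/dL is not reproduced.
3. Gap: 2.87 − 2.65 = 0.22 mmol/L; 11.5 − 10.62 = 0.88, about 0.9 mg/dL. The ratio is 2.869 / 2.65 = 1.083, so the mg/dL limit lies about 8.3% above the mmol/L limit.

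**Could rounding or another unit explain it?**

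- Figures that round to 11.5 mg/dL (11.45 to 11.55) correspond to 2.857 to 2.882 mmol/L.
- Figures that round to 2.65 mmol/L (2.645 to 2.655) correspond to 10.60 to 10.64 mg/dL.
- In mEq/L, 11.5 mg/dL is 2 × 115 / 40.078 = 5.74.
- The two limits would agree only with a molar mass of 115 / 2.65 = 43.4 g/mol.

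None of these reconciles them.

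**What the gap does.** Take a newly developed corrected calcium of 2.75 mmol/L, which is 2.75 × 40.078 / 10 = 11.02 mg/dL, attributed only to the myeloma in a subject who meets no other PD criterion. Read in mmol/L it exceeds 2.65 and is PD. Read in mg/dL it is below 11.5 and is not. The same holds for any such value above 2.65 and up to 2.87 mmol/L (10.6 to 11.5 mg/dL). Outside the band the two limits agree.

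**The case against.** The conversion error itself is hard to contest. The case on the other side concerns its reach, and much of that stands.

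- **A reader might infer that the same measurement is in fact classified differently at different sites.** The documents do not show this. They give no site's calcium unit, and all sites are in Germany and Austria. If every site reports in one unit, one limit applies throughout and no between-site difference arises. Read literally, *or* means that either limit suffices; 2.65 mmol/L then always governs and 11.5 mg/dL is dead text. The figures still disagree, and a site working in mg/dL would naturally apply the mg/dL figure.
- **A reader might infer that any calcium in the band changes the outcome.** It does not. The hypercalcemia must be new and attributable to the myeloma alone, and no other PD criterion may be met.
- **Response evaluation is said to rest on M-protein and free light chains** (Protocol 11.1.1, SAP 7.3.3), without naming calcium. Table 14 nevertheless keeps hypercalcemia as sufficient for PD, and Protocol 11.1.1 defines progression by that table.
- **SAP 7.3.3.2 and 7.3.3.3 disregard an isolated PD** that did not stop treatment and was disproved at the next non-missing assessment. That removes some transient calls. It does not remove a PD that is the last tumor assessment, which counts without confirmation.
- **The mismatch may come from the published criteria** on which Table 14 is based. That cannot be checked from these documents, and it would not make the two limits agree.
- **The primary endpoints do not use PD.** They are the maximum tolerated or recommended dose and regimen, adverse events and immunogenicity. The affected endpoints are secondary or additional, and their analysis is descriptive.

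**Conclusion.** The error is certain: Table 14 presents two limits as one, and they differ by 0.22 mmol/L (0.9 mg/dL), about 8%. This rests only on the molar mass of calcium, and no plausible value changes it.

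The consequence is conditional. Investigator-assessed progression may depend on the unit read, for subjects in the 2.65 to 2.87 mmol/L band whose hypercalcemia is new, due only to the myeloma, and the sole criterion met. How many such subjects there are cannot be derived from the documents, but the number is probably small.

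Two further inferences are not supported. The documents hold no data on how specific either limit is for progression. The Durie-Salmon table in Protocol 18.6 does not help choose between the limits: it stages disease at screening, does not say that its calcium is corrected, and has no bearing on PD. The point is therefore a threshold to reconcile, with limited expected effect on secondary and additional descriptive results. Which limit is clinically right is not decided here.

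**What to change.** 1. Reconcile Table 14 to a single governing limit with a correct conversion: either 11.5 mg/dL with 2.87 mmol/L, or 10.6 mg/dL with 2.65 mmol/L. The sponsor should choose, and notify all sites. This costs a one-line protocol correction and a site notice.
2. Because SAP 7.3.3 ties each assessment to the protocol version then in force, the correction will not alter calls already made. Review recorded PDs for any that rest on calcium alone with a value between 2.65 and 2.87 mmol/L. SAP 7.3.3 mentions only the response category and the progression date, and the documents do not show that the eCRF records the triggering criterion, so this may need case review.
3. Only if such cases are found, list them with their SI values and add a PFS and TTP sensitivity analysis that applies the single limit. Calcium and albumin are both in the chemistry panel (Protocol Table 11), but the protocol gives no formula for corrected calcium, so the listing must state the one used. If no case is found, a sentence in the study report is enough.

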## **18.4** New York Heart Association Functional Classification

The NYHA criteria for classifying the extent of cardiac failure are presented in Table 15.

 Table 15
 Criteria for NYHA Functional Classification

NYHA Class	Criteria
Ι	No symptoms and no limitation in ordinary physical activity. Shortness of breath
	when walking, stair climbing, etc.
II	Mild symptoms (mild shortness of breath and/or angina pain) and slight limitation
	during ordinary activity.
III	Marked limitation in activity due to symptoms, even during less-than-ordinary
	activity (e.g., walking short distances, approximately $> 20 - 100$ meters).
	Comfortable only at rest.
IV	Severe limitations. Experiences symptoms even while at rest, mostly bedbound
	patients.

Abbreviation: NYHA = New York Heart Association

# 18.5 Karnofsky Performance Status

The Karnofsky criteria for assessing performance status are presented in Table 16.

Table 16Criteria for Karnofsky Performance Status

Score (Percent)	Criteria
100	Normal, no complaints, no evidence of disease
90	Able to carry on normal activity; minor signs or symptoms of disease
80	Normal activity with effort; some signs or symptoms of disease
70	Cares for self, unable to carry on normal activity or to do active work
60	Requires occasional assistance, but is able to care for most of his/her needs
50	Requires considerable assistance and frequent medical care
40	Disabled, requires special care and assistance
30	Severely disabled, hospitalization indicated; death not imminent
20	Very sick, hospitalization indicated; death not imminent
10	Moribund, fatal processes progressing rapidly
0	Dead

